# 15 Treatment Compliance and Exposure

This bioequivalence study is a single oral dose administration.

All dosing and treatment compliance, including the date and time of drug administration, will be recorded on "B2 Dosing" and "C2 Dosing" CRFs pages and will not be presented in the CSR.

# **Endpoint Evaluation**

### 16.1 Primary Endpoint Analyses

The primary endpoints are  $C_{max}$  and  $AUC_{0-t}$  for metformin concentration in plasma.

The statistical method for testing bioequivalence is ANOVA for 2-period, 2-sequence, 2-treatment cross-over comparing  $AUC_{0-t}$  and  $C_{max}$  after ln transformation of the original values.

Bioequivalence is concluded if the 90% confidence interval of the Test/Reference geometric means ratio is in the range of 80.00-125.00% for AUC0-t and Cmax. This acceptance criterion is according to the Guideline on the Investigation of Bioequivalence, EMA, London, 2010; ASEAN Guideline for the Conduct of Bioequivalence Study, Lao PDR, 2015; and Indonesian guidelines, *Pedoman Uji Bioekivalensi, Badan Pengawas Obat dan Makanan (BPOM)*, Jakarta, 2015, page 37-38.

Phoenix® WinNonlin (PPD ) will be used to perform the statistical analyses of AUC0-t and Cmax using analysis of variance (ANOVA) with the factors TREATMENT, PERIOD, SEQUENCE and SUBJECT(SEQUENCE) after transformation of the data to their natural logarithmic (ln) values. Mean treatment differences will be estimated using the ANOVA model above. 90% confidence intervals will be computed for the treatment differences based on the residual error term. Differences and CIs will result in ratios and corresponding CIs after back-transformation.

# 16.2 Secondary Endpoint Analyses

The secondary endpoints are  $t_{max}$ , AUC0-inf and  $t_{1/2}$  for metformin concentration in plasma.

The difference in  $t_{max}$  will be analyzed non-parametrically on the original data using Wilcoxon matched-pairs test.

The  $t_{1/2}$  difference will be analyzed using Student's paired t-test or Wilcoxon matched-pairs test depending whether the differences of the paired data were distributed normally or not (tested with *Kolmogorov-Smirnov*).

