11.2 Statistical Analysis

Safety data will be evaluated for all subjects who received at least one dose of study medication. The data from subject(s) who received concomitant medication(s) or experienced diarrhea or vomiting during PK blood sampling periods, which could render the plasma concentration-time profile unreliable as stated on section 5.3.3, may be excluded

for that period from the pharmacokinetic analysis and statistical evaluation. The decision to exclude is made before bioanalysis.

Statistical analyses will include data from all subjects who have valid primary endpoints available for both periods of the study. The plasma concentrations obtained from the bioanalytical laboratory for subjects who have been withdrawn from the study due to adverse events or as list on section 5.3.3 will not be used for statistical evaluation.

The statistical method for testing bioequivalence is ANOVA for two-period, two-sequence, two-treatment cross-over comparing AUC_{0-t} and C_{max} after logarithmic (ln) transformation of the original values. The terms to be used in the ANOVA model are sequence, subject within sequence, period, and formulation.

Bioequivalence is concluded if the 90% confidence interval of the Test/Reference geometric means ratio is in the range of 80.00-125.00%, for AUC_{0-t} and C_{max} . This acceptance criterion is according to the Guideline on the Investigation of Bioequivalence, EMA, London, 2010; ASEAN Guideline for the Conduct of Bioequivalence Study, Lao PDR, 2015; and *Indonesian guidelines, Pedoman Uji Bioekivalensi, Badan Pengawas Obat dan Makanan (BPOM), Jakarta, 2015, page 37-38.*

Non-compartmental standard methods computation of PK parameters will be performed. Details will be provided in the final study report. Phoenix® WinNonlin (Version 8.0 or higher) (PPD [REDACTED]) will be used to perform the statistical analyses of AUC_{0-t} and C_{max} using analysis of variance (ANOVA) after transformation of the data to their natural logarithmic (ln) values. Mean treatment differences will be estimated using the ANOVA model above. 90% confidence intervals will be computed for the treatment differences based on the residual error term. Differences and CIs will result in ratios and corresponding CIs after back-transformation.

The difference in t_{max} will be analyzed non-parametrically on the original data using Wilcoxon matched-pairs test.

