The $t_{1/2}$ difference will be analyzed using Student's paired t-test or Wilcoxon matched-pairs test depending whether the differences of the paired data were distributed normally or not.

Descriptive Statistic

Arithmetic means, standard deviations, minimum, maximum, median, and coefficients of variation will be calculated for the parameters listed in section 11.1.

Plasma concentration-time profile will be provided in linear and log scale for mean curves with standard deviation and individual curve in each subject.

Demographic data will be provided as summary tables with information of mean, minimum value and maximum value presented.

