#### Secondary objective:

- To compare pharmacokinetic parameters of metformin after single dose administrations of test and comparator (reference) drugs.
- To examine the safety and tolerability of metformin after single dose administrations of test and comparator (reference) drugs.

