#### **Randomization Sequence**

Sequence 1 = TR (24 subjects)

Sequence 2 = RT (24 subjects)

The randomization code is tabulated for all subjects according to block randomization with a block size of 4 (Dixon & Massey, 1969, page 449). Subjects will be randomly allocated to one of the 2 treatment sequences (TR or RT) based on their assigned subject number. The randomization to a treatment sequence will be performed before the first period of the study.

Each study drug (test and reference drug) will be placed in a sealed envelope indicated with the subject number and its intended period and segregated in different labeled boxes kept in a limited access drug storage room. The study drugs will be dispensed to the study subjects by an

unblinded pharmacist prior to time of dosing. The randomization will be balanced according to subject number and the randomization code will be kept under controlled access. The clinical personnel administering the study drugs and the subjects are not blinded. The randomization code will not be available to the bioanalytical personnel (blinded for bioanalytical facility) till code breaking.

Code breaking will be performed after database lock i.e. after analysis of all blood samples has been finalized, and all PK parameters have been calculated. Sponsor's green light has to be obtained prior to code breaking, upon satisfying pre-defined conditions.

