# 11 General Specifications for Statistical Analyses

PK concentration data will be descriptively summarized using: number of non-missing observations (N), arithmetic mean (Mean), standard deviation (SD), coefficient of variation (CV%), minimum (Min), median (Median) and maximum (Max).

PK parameter data will be descriptively summarized using: number of non-missing observations (N), arithmetic mean (Mean), standard deviation (SD), coefficient of variation (CV%), minimum (Min), median (Median), maximum (Max), geometric mean, and the 90% confidence interval.

For the calculation of descriptive statistics and the statistical analysis, values as presented in the data listing will be used. Minimum and maximum will be presented to the same decimal precision as collected. Mean, median, and SD estimates will be presented to one decimal place

more than the precision of the data collected. CV will always be reported to 1 decimal place. Derived parameters will be reported using similar precision to those from which they were derived.

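### The secondary PK analyses give tmax and t½ paired tests that ignore period and carry no T/R estimate or interval, and give AUC0-inf no T/R contrast

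*SAP*

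**What the plan says.** One secondary objective (SAP 6) reads "To compare pharmacokinetic parameters of metformin after single dose administrations of test and comparator (reference) drugs". SAP 16.2 names three secondary endpoints and treats them as follows.

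- **tmax:** a Wilcoxon matched-pairs test on the untransformed values. Protocol 11.2 likewise has it "analyzed non-parametrically on the original data using Wilcoxon matched-pairs test".
- **t½:** in Protocol 11.2 the "difference will be analyzed using Student's paired t-test or Wilcoxon matched-pairs test", depending on normality. SAP 16.2 likewise gives a paired t-test or a "Wilcoxon matched-pairs test depending whether the differences of the paired data were distributed normally or not", and adds that normality is checked with Kolmogorov-Smirnov.
- **AUC0-inf:** no analysis sentence. SAP 16.3 gives only its derivation.

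The tmax and t½ wording also stands in the protocol synopsis, SAP 6 (Statistical Methods) and SAP 8.

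The primary endpoints, AUC0-t and Cmax, get an ANOVA "with the factors TREATMENT, PERIOD, SEQUENCE and SUBJECT(SEQUENCE) after transformation of the data" to the ln scale (SAP 16.1), with a 90% CI for the treatment difference back-transformed to a ratio.

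For all PK parameters Protocol 11.2 adds descriptive statistics: "Arithmetic means, standard deviations, minimum, maximum, median, and coefficients of variation will be calculated for the parameters listed in section 11.1". SAP 11 extends the list to "minimum (Min), median (Median), maximum (Max), geometric mean, and the 90% confidence interval", without saying what that interval is for. SAP 9 reports no departure from the protocol's analyses.

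**The concern.** Two separate points arise.

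1. **Missing contrasts.** A comparison of formulations needs the size of the difference and its uncertainty. As written, tmax and t½ yield a p-value and per-treatment summaries, and AUC0-inf yields summaries only. A non-significant p-value does not show that two products are similar, which is why the primary analysis uses an interval. Under SAP 5, a T/R ratio for AUC0-inf added later would have to be reported as unplanned.

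2. **Period.** The primary model adjusts for period, but the secondary tests on the same crossover data do not. A period effect enters T−R with opposite signs in the two sequences. It widens the spread of the pooled differences and, if the sequences end unequal, shifts their mean.

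Only the secondary objective is at stake.

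**Working it through.** The plan gives no power or precision figure for the secondary endpoints, so there is none to reproduce.

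**Inputs from the documents.** 24 subjects per sequence (SAP 7, Randomization Sequence); four extra subjects to cover drop-outs, with no replacement (SAP 7), so sequences can end unequal; the sampling times in Protocol 9.1.

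**Assumed, because the documents give neither.** Period effect p = 0, 0.25, 0.5 or 1 and true shift d = 0.5, both in SDs of the within-subject T−R difference; two-sided 5% level.

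**Model.** T−R has mean d − p in TR and d + p in RT, with SD 1. A sequence effect cancels in T−R, so the missing sequence term has no consequence of its own.

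**Shift of the unadjusted mean** = p × (nRT − nTR)/N.
- 24/24 or 22/22: 0.
- 23/21 or 21/23: 2/44 = 0.045 × p in size.
- 24/20 or 20/24: 4/44 = 0.091 × p in size.

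**Chance of each split** if four drop-outs fall at random: C(24,i) × C(24,4−i) / C(48,4). This gives 22/22 39%, 23/21 and 21/23 25% each, and 24/20 and 20/24 5.5% each. Some imbalance therefore has probability 1 − 0.39 = 61%.

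**Loss of precision.** With equal sequences the variance of the pooled differences is about 1 + p², so the paired-t interval widens by about √(1 + p²) = 1, 1.03, 1.12 and 1.41. At 24/24 the 90% half-width is 0.24, 0.25, 0.27 and 0.34 SD, against 0.24 for the ANOVA contrast.

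**Power of the planned signed-rank test** (%, 20,000 simulations per cell, standard error at most about 0.35 points). The comparison is a rank-sum test of the period differences between sequences.

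| TR/RT | p = 0 | 0.25 | 0.5 | 1 | Rank-sum |
|---|---|---|---|---|---|
| 24/24 | 91 | 90 | 86 | 66 | 91 |
| 22/22 | 89 | 88 | 83 | 61 | 88–89 |
| 23/21 | 89 | 86 | 79 | 49 | 88–89 |
| 21/23 | 89 | 89 | 87 | 72 | 88–89 |
| 24/20 | 89 | 84 | 75 | 38 | 88–89 |
| 20/24 | 89 | 90 | 90 | 82 | 88–89 |
| Averaged over four random drop-outs | 89 | 88 | 83 | 61 | 88 |

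At a two-sided 10% level and 24/24 the signed-rank figures are 95, 95, 93 and 82%, against 95%. Paired-t power for t½ at 24/24 is 92, 91, 88 and 72%, against 92% for the ANOVA contrast.

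**Type I error of the signed-rank test** for the same four p: 4.7, 4.3, 2.6 and 0.4% at 24/24; 5.2, 4.5, 3.6 and 1.4% at 24/20; 5.1, 4.4, 3.5 and 1.4% at 20/24. Rank-sum: 4.5–5.0%. Within simulation error the planned test never exceeds its nominal level; a period effect makes it conservative.

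**Ties in tmax.** Lognormal tmax was moved to the nearest sampling time at 24/24, with medians 4, 5 and 7 h, T 15% later and between-subject log-SD 0.15 (all assumed). Protocol 2.3.1 gives 5 h for 1500 mg and 7 h for XR 500, but nothing for 750 mg fasted. With within-subject log-SD 0.20 and period ratios 1.0, 1.1 and 1.2, signed-rank power is 88–89, 85–87 and 80%, against 87–89, 88 and 88%. With log-SD 0.30 it is 57–58, 55–56 and 49–50%, against 57–58, 56–57 and 55%. Ties do not change the picture.

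**What an AUC0-inf ratio would show.** 90% CI = exp(±t(0.95, 42) × √ln(1 + CV²) × √(2/44)) at 44 evaluable subjects and observed ratio 1. The planned CVs are redacted, so these are assumed: CV 15% gives 94.79–105.49%, 25% gives 91.55–109.23%, and 30% gives 90.01–111.10%.

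**The case against.** **A period effect is not in evidence.** Nothing in the documents reports or expects one. Washout is at least 7 days against a half-life of about 6.5 h (168/6.5, about 26 half-lives), and meals, fasting and sampling are the same in both periods. At 24/24 with 0.25 SD the loss is about 1 point. The large losses need 0.5–1 SD, and the 38% figure also needs a 24/20 split. This stands: the practical cost of ignoring period is unproven and may be nil.

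**Power is a weak yardstick here.** The plan sets no level, power target or decision rule for these tests, and the 0.5 SD shift has no source in the documents. This also stands, and the power figures are only illustrative.

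**Adjustment can lose slightly.** At 20/24 with 0.25 or 0.5 SD, signed-rank has 90% in both cases against 88%. True, but small.

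**SAP 11 may already supply the interval.** The only 90% CI defined elsewhere in the SAP is the treatment ratio interval, so a T/R reading is possible. But the item sits in a list of descriptive statistics and names no contrast. At best it is ambiguous.

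**To compare need not mean an interval.** Tests plus summaries arguably meet a secondary objective for tmax and t½. For AUC0-inf there is not even a test.

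**Conclusion.** The concern holds as an optional improvement. The textual part needs no assumption: no T/R estimate or interval is specified for tmax or t½, and AUC0-inf, a named secondary endpoint, has no T/R contrast. The period part is conditional. The tests are valid and cost nothing without a period effect. Under the stated assumptions, signed-rank power at 24/24 falls from 91% to 86% at 0.5 SD and to 66% at 1 SD. With four random drop-outs it falls from 89% to 83% and 61%. The bioequivalence decision, sample size and procedures are unaffected.

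**What to change.** Before code breaking, amend SAP 16.2 and the matching wording in SAP 6 and SAP 8:

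- **tmax:** compare within-subject period differences (period 1 minus period 2) between TR and RT with a rank-sum test. Report half the Hodges-Lehmann shift, with its 90% CI, as the T−R difference in hours.
- **t½:** apply the SAP 16.1 ANOVA to ln(t½) and report the T/R ratio with 90% CI. The Kolmogorov-Smirnov pre-test is then unnecessary.
- **AUC0-inf:** use the same ANOVA on the ln scale, with geometric mean ratio and 90% CI, labelled supportive and outside the bioequivalence decision.
- **SAP 11:** state what the 90% CI in the descriptive list refers to.
- **SAP 9:** record the departure from Protocol 11.2 and the synopsis.

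The cost is SAP text and a few more output lines from data already collected. The t½ result becomes a ratio instead of a difference in hours. With no period effect, rank-sum power is about 0.3 points lower at 24/24 and about 1 point lower at 24/20 or 20/24. At 20/24 with a period effect of 0.25–0.5 SD it is 1.5–2.4 points lower. If the sponsor prefers to keep the planned tests, the estimates, intervals and AUC0-inf ratio can still be added alongside them.

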#### 16.3 Estimation of Individual PK Parameters

Pharmacokinetic parameters will be calculated using standard non-compartmental methods Phoenix® WinNonlin® version 8.0, or higher (PPD ) as defined below

Symbol	Definition
AUC 0-t	area under plasma concentration curve from administration to last observed concentration at time t
AUC 0-inf	Area under plasma concentration from time zero (dosing time) extrapolated to infinite time. AUC 0-inf will be calculated as AUC 0-t + $C_t/k_e$ , where $C_t$ is the last observed plasma concentration; $k_e$ is the terminal elimination rate constant and will be determined by least-squares regression analysis during the terminal log-linear phase of the concentration–time curve
C max	Maximum observed plasma concentration
t 1/2	Terminal phase half-life time. $t_{1/2} = \ln (2)/k_e$
t max	The time to reach the maximum observed concentration (C max )

All concentration values below the quantification limit (BQL) will be set to zero for all pharmacokinetic and statistical calculations.

# 17 Safety Evaluation

In this study, safety will be assessed by qualified study personnel by evaluating reported adverse events, clinical laboratory test results, vital signs measurements, ECG findings, physical examination findings (including body weight and height measurements), and use of concomitant medication. Adverse events, laboratory tests and vital signs will be recorded in the CRF and tabulated in the CSR.

#### 17.1 Adverse Events

An adverse event is any untoward medical occurrence in a subject or clinical investigation subject administered a pharmaceutical product, regardless of causal relationship with this treatment. An AE can therefore be any unfavorable and unintended sign (including an abnormal laboratory finding), symptom, or disease temporally associated with the use of a medicinal product, whether or not considered related to the medicinal product. WHO-ART will be used as coding dictionary of adverse events. All adverse events will be listed.

The following summary tables will be presented for treatment emergent AEs:

- Summary of TEAEs by SOC, PT and treatment
- Summary of TEAEs by SOC, PT, intensity and treatment

• Summary of TEAEs by SOC, PT, causality and treatment

The denominator for the percentages in the summaries will be the number of subjects in the safety population for each treatment.

# 17.1.1 All Adverse Events

All of adverse events occurred during the study will be listed in the CSR (Table 3). An overview of all adverse events will be presented in Table 4. Adverse reaction (from test and comparator drug) would be categorized as unrelated, unlikely, possibly related, probably, and definite related based on literature data and pharmacokinetics profile (Table 5). All adverse events, regardless of severity, will be followed up and recorded by the investigator. All adverse events will be recorded in the CRF and tabulated in the CSR.

Table 3 List of Adverse Events Occurred

	Listing All Adverse Events											
Period (I or II) Treatment	Subject No.	System Organ Class/ Preferred Term/ Reported Term	Serious criteria	Start Date	End Date (AE Duration)	Severity	Relationship to IMP	Action taken with study treatment	Other action taken	Outcome	Comment	
Period I Reference		/ / 	No	yyyy-mm-dd, hh:mm	yyyy-mm-dd, hh mm (dd,hh,mm)							
Period 2 Test												

Table 4 Overview of all Adverse Events (by Group and Overall)

	Test Drug (N=xx)	Comparator Drug (N=xx)	All (N=xx)
Subjects with any AE (%)	0 (00.0%)	0 (00.0%)	0 (00.0%)
Number of all AEs	0	0	0
Number of treatment emergent AEs	0	0	0
Drug-related AEs	0	0	0
Serious AEs	0	0	0
Withdrawal due to AEs	0	0	0

**Table 5** Adverse Events: Number Observed

Adverse event	vent Mild		Moderate			Severe				Total						
	Definite	Probably	Possibly	Unlikely	Unrelated	Definite	Probably	Possibly	Unlikely	Unrelated	Definite	Probably	Possibly	Unlikely	Unrelated	
Test Drug																
SOC 1																
	0	0	0	0	0	0	0	0	0	0	0	0	0	0	0	0 (0.0%)
SOC 2																
•••	0	0	0	0	0	0	0	0	0	0	0	0	0	0	0	0 (0.0%)
SOC 3																
•••	0	0	0	0	0	0	0	0	0	0	0	0	0	0	0	0 (0.0%)
Others																
•••	0	0	0	0	0	0	0	0	0	0	0	0	0	0	0	0 (0.0%)
Comparator Drug																
SOC 1																
•••	0	0	0	0	0	0	0	0	0	0	0	0	0	0	0	0 (0.0%)
SOC 2																
•••	0	0	0	0	0	0	0	0	0	0	0	0	0	0	0	0 (0.0%)
SOC 3																
•••	0	0	0	0	0	0	0	0	0	0	0	0	0	0	0	0 (0.0%)
Others																
	0	0	0	0	0	0	0	0	0	0	0	0	0	0	0	0 (0.0%)

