#### **Study Subjects**

Forty-eight (48) healthy adult male and female subjects

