# 10.2 Definition of Analysis Sets and Subgroups

#### Safety Analysis Set

The safety analysis will include all subjects who have received at least one dose of the investigational product and have had one subsequent safety assessment.

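### SAP Table 5 attaches a percentage to counts of adverse events, while the only denominator given in section 17.1 is subjects, with no once-per-subject rule

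*SAP*

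**What the plan says.** SAP section 17.1 promises three summaries, introduced by "The following summary tables will be presented for treatment emergent AEs": by SOC and preferred term, then with intensity added, then with causality added, each by treatment. It then sets the denominator: "The denominator for the percentages in the summaries will be the number of subjects in the safety population for each treatment".

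Section 17.1.1 supplies the shells. Table 5 is titled "Adverse Events: Number Observed". For each product and each event row it has 15 cells (three severities by five causality categories), followed by a Total shown as a count with a percentage in brackets. It has no N in the header, no footnote on the percentage, and no rule for a subject who has the same event more than once.

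Table 4, in the same section, keeps the two units apart. Its first row, "Subjects with any AE", has a percentage, and its columns carry N. The next row, "Number of all AEs", is a plain count. The remaining rows, including the one for withdrawals, are also plain counts.

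The safety set is defined in section 10.2: "The safety analysis will include all subjects who have received at least one dose of the investigational product and have had one subsequent safety assessment".

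**The concern.** By its title, Table 5 counts events. The only denominator that the adverse event section offers is subjects. A programmer who follows both would divide events by subjects. That quotient is a mean number of events per subject written as a percentage. It equals the proportion of subjects affected only when every affected subject contributes exactly one event to the row. Nothing in section 17.1 or 17.1.1 limits a subject to one entry, for example at the worst severity or the strongest causality, so one mild and one moderate episode of the same term would fall in two cells and both would enter the Total.

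Comparing the safety and tolerability of the two products is a stated secondary objective (SAP section 6). Table 5 is the only shell that shows a percentage by product at the level of the individual event, so a reader would naturally take it as an incidence and compare products on it.

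**Working it through.** The plan has no figure to reproduce: the shells contain only zeros. The check is therefore on units, followed by arithmetic on assumed counts.

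**Inputs**

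- Numerator of Table 5: events observed (table title, section 17.1.1).
- Denominator: safety-population subjects for each treatment (section 17.1).
- N: the SAP plans "Forty-eight (48) healthy adult male and female subjects" in a two-period crossover, so at most 48 per product.
- Number of subjects affected (S) and number of events (E) in a row: not given anywhere, so assumed below.

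**Formulas**

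- Table 5 as laid out: 100 × E / N
- Share of subjects affected: 100 × S / N
- Ratio of the first to the second: E / S, the mean number of events per affected subject

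**One subject, three events, N = 48**

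- As laid out: 100 × 3 / 48 = 6.25%, printed as 6.3%.
- Subjects affected: 100 × 1 / 48 = 2.08%, printed as 2.1%.
- Difference: 100 × 2 / 48 = 4.2 percentage points. Each extra event adds 100 / 48 = 2.1 points.

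**Six affected subjects, over a range of repeats (assumed)**

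| Events per affected subject | N = 48: as laid out | N = 48: subjects | N = 44: as laid out | N = 44: subjects |
|---|---|---|---|---|
| 1 | 12.5% | 12.5% | 13.6% | 13.6% |
| 1.5 | 18.8% | 12.5% | 20.5% | 13.6% |
| 2 | 25.0% | 12.5% | 27.3% | 13.6% |
| 3 | 37.5% | 12.5% | 40.9% | 13.6% |

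The N = 44 columns, using the SAP's evaluable number, show that the choice of N matters little. The mean number of events per affected subject drives the discrepancy, and at one event each there is none.

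**Could the percentage mean something else?** A share of all events on that product is conceivable, but the SAP does not say so, and it would conflict with section 17.1 if Table 5 is one of the summaries meant there. If Table 5 is not one of them, its percentage has no defined denominator and the three promised summaries have no shell.

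**The case against.** The strongest reply is that the denominator sentence does not name Table 5. It follows a list of three treatment-emergent summaries, whereas Table 5 is in the next subsection, is not restricted to treatment-emergent events, and crosses severity with causality, which none of the three does. That is correct, and the link is an inference: Table 5 falls under 17.1 and is the only shell laid out by SOC, intensity, causality and treatment. It would therefore be too much to say that the SAP fixes the denominator of every percentage. What stands is that the percentage is either events over subjects or undefined, and the shell needs correcting in both cases.

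The second reply is that much of this is covered elsewhere. Table 4's first row is a valid subject-level rate by product. Table 3 lists every event by subject and treatment, so repeats can be seen and recounted. Tables 6 and 8 list drop-outs and serious events by subject. This stands, and it limits the consequence.

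The third reply is that repeats may be rare. Each product is given once, and protocol section 5.3.3 removes a subject who vomits during sampling from the rest of the study. A reader might infer from the diarrhea criterion in the same section, with its count of loose stools, that repeat gastrointestinal records are to be expected. The text does not support this: there the count defines a diarrhea event, and nothing makes each stool a separate record. Repeats remain possible, since protocol section 7.3 schedules adverse event monitoring at seven post-dose times per period and the form in Appendix A gives each event its own row with onset, end, intensity and causality.

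Finally, event counts in a severity-by-causality grid are a legitimate display. That is so. The objection here is only to the percentage beside them.

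**Conclusion.** The point holds as a mismatch of units in one table shell. Taken with section 17.1, Table 5's percentage is events over subjects and overstates the share of subjects affected whenever a subject has the same term more than once on one product. The factor is the mean number of events per affected subject. One subject with three events at N = 48 gives 6.3% instead of 2.1%.

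This rests on reading the section 17.1 denominator as applying to Table 5, and the event counts used are assumptions. The actual size is unknown and probably small with one dose per product.

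A reader might infer that the reported rates will be materially inflated, or that a false difference between products will appear. The documents do not support this: they give no expected event counts, and the larger figures in the table above require every affected subject to have several events. A value above 100% is possible arithmetically, but it would need more than 48 events in one row for one product. The bioequivalence conclusion is unaffected, because section 16.1 rests it on AUC0-t and Cmax alone.

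**What to change.** - **Table 5:** keep the severity-by-causality cells and the Total as event counts, without a percentage. Add a separate column of subjects n (%) that counts each subject once per SOC and once per preferred term on each product. Put N for each product in the header.
- **Intensity and causality summaries promised in section 17.1:** state that a subject is counted at worst severity in the intensity summary and at strongest causality in the causality summary. Do not apply both rules jointly in the Table 5 grid: a subject with one severe unrelated event and one mild definite event would then appear as severe and definite, a cell that no event occupied.
- **Table 4:** label the withdrawal row as subjects n (%).

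The cost is an edit to two table shells, the counting rules for the promised summaries, and the associated programming. No new data are needed.
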